administer in a busy clinic setting. The **PEG-3** is derived from the Brief Pain Inventory. (38, 39) It has internal reliability and construct validity, and responsiveness among primary care patients. Each item (Pain, Enjoyment, General Activity) is scaled 0-10 with the final score being the average of the 3 individual item scores. The score is best used to track changes in an individual's score over time. A decrease in score over time with the initiation of therapy is considered responsive to treatment. **PHQ-4** consists of a two-item measure of depression and two-item measure of anxiety. (40) The scale has internal reliability, construct validity and factorial validity. The score indicates normal (0-2), mild (3-5), moderate (6-8), or severe symptoms (9-12). A score ≥ 3 on the depression subscale identifies potential cases of depressive disorders while a cut-point of ≥ 3 on the anxiety scale identifies potential cases of generalized anxiety, panic, social anxiety and posttraumatic stress disorders. Increasing scores are associated with multiple domains of functional impairment and have a strong dose response relationship with disability days and physician visits. The PHQ-4 is not diagnostic and further inquiry to establish the presence of a mental disorder is warranted. If PHQ-4 is ≥ 3 , documentation of **PHQ-9** (41) and **GAD-7** (42-45) is recommended for detailed screening and subsequent monitoring of symptoms should a formal diagnosis be made. Patient responses to questionnaire items are documented via Epic's flowsheet tool to facilitate capturing this information as structured data.

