C.4.2. Stepped Care for Opioid Collaborative Care Management (Stepped Opioid CCM). Our preliminary analysis of opioid prescriptions substantiates that most patients receiving chronic opioid therapy in primary care have comorbid psychiatric diagnoses (Section 3.1). *Stepped opioid CCM is an additional component of the overall opioid management strategy* (EMR CDS+ stepped opioid CCM). It is designed to systematically expand care options for patients who have comorbid depression, anxiety or psychosocial issues (e.g. problems with relationships, work or school) that may complicate opioid therapy and recovery. Our collaborative care team will be composed of a community health worker (CHW), a licensed clinical social worker (LCSW), and a clinical pharmacist (PharmD). Such personnel are already used across the system, and we will train existing staff in study procedures. As previously described in the Study Design Overview, we will randomize the order in which the service becomes available across 5 geographic regions and initiate service in each region in 3-month intervals over a 15-month period. We will physically locate the service in the 5 clinic locations with the highest opioid prescription rates. However, all clinics within each region can refer patients for care. To control the fidelity of services provided during this study, only CHW-LCSW-PharmD personnel trained in the study protocol will provide stepped opioid CCM.

Figure 2 summarizes our model of care. This intervention is modeled after [name] previous research on integrating mental/behavioral in primary care.(34) Eligibility criteria for stepped opioid CCM include PHQ-9 or GAD-7 ≥ 10 , clinical diagnosis of depression or anxiety disorder, psychosocial concerns, and chronic pain requiring opioid therapy. We will use the EMR registry and bulk order function to notify providers of eligible patients within their panel. When providers sign off on the referral orders, a list of patients will automatically be generated for clinic personnel to facilitate scheduling baseline assessments.

Figure 2. Collaborative Care Model for Co-Morbid Depression, Anxiety, Psychosocial Disorders and Chronic Non-Cancer Pain

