Patients or proxy account users (family/friends/caregivers) may click on the notice to be taken to the Research Studies/Available Studies page to review the study’s recruitment message. Patients will be able to select “I’m Interested” or “No Thank You” to whether they would like to notify the study team that they may want to participate. The responses, both positive and negative, are populated in the study coordinator and principal investigator’s Epic InBasket, in the system’s pre-labeled **Research Recruitment** folder.

Interested Patients Workflow

1. The study coordinator will review the Research Recruitment folder for patients with “**Completed**” enrollment status. “Completed” is the default enrollment status based on the recruitment notice being read and “**I’m Interested**” being selected by the patient. **If the patient has not responded to the notice**, the default enrollment status is “**Identified**”. Figure 2 is an image of the of Enrollment Status Categories in Epic.

Figure 2 Epic Enrollment Status Categories

2. The CHW or study team member will conduct a **brief chart review** to look for anything in the chart that would deter or defer patients from following up (e.g. admission, prolonged/terminal illness).
3. If no concerns, or red flags, the CHW or study team members (i.e. only Ochsner employees or Ochsner medical students) will call the patient to explain the program and invite them to complete the screening assessment with the PHQ9 and GAD7. If the patient screens eligible and is agreeable, the CHW or study team member will complete the intake procedures (PROMIS and scheduling appointment with the LCSW). Patients may have the option to

complete screening and/or intake by phone or if available, in-person (e.g. upcoming clinic appointment).

4. When **the study team/CHW-administered PHQ9/GAD7 score meets the threshold (either score ≥ 10)**, the PCP will be notified of their patient's program eligibility or ineligibility and will be given instructions on how to place the referral mentioned above.

Screening Log

The study team will add all patients screened for eligibility to the Research Study activity in Epic and document the screening date (i.e. start date), the recruiter name (i.e. CHW), the reason for ineligibility or decline, and enrollment status (e.g. enrolled, screen failed, ineligible-did not meet full criteria, declined).

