#### **5. Statistical Analysis**

Outcomes data were observed and collected in two time periods, pre-index and post-index. For the behavioral health group, the index date was defined as the date of enrollment during the study recruitment period (April 2019 to December 2021). For EMR-CDS usual care group, the index date is the first date within the study enrollment period at which a patient had been prescribed opioid medications for 90 of the previous 120 days.

Potential participants in the control arm of the study were identified from the chronic opioid health maintenance registry within the electronic health record system and propensity score matched to patients enrolled in the behavioral health arm. Baseline variables in the propensity score model were age at index event date, sex, race/ethnicity, average MEDD, anxiety, depression, and Charlson comorbidity index score. Average MEDD was calculated from opioid medication orders in the 12-month pre-index period. MEDD is calculated by determining the total daily amount of a prescribed opioid, multiplying the dose of the opioid by a conversion factor to ascertain morphine milligram equivalents and then adding up the converted dosage. Anxiety, depression, and Charlson comorbidity scores were determined from pre-index encounter diagnoses, historical problem lists, and PHQ-9/GAD-7 scores  $>10$  documented within the electronic health record.

Study outcomes were observed and collected in two 12-month time periods defined relative to the index date, pre-index and post-index, resulting in a 2-dimensional vector of repeated measures for each outcome from each patient. All outcome models for repeated measures incorporate a random effect with unstructured covariance matrix to model within-patient variability. It was assumed that patients remained in the health system from their first observed encounter through the end of the study period. A difference-in-difference approach was utilized in which outcomes were assessed as the change in group differences from pre- to post-

index. The model included fixed effects for study group, time (pre-index, post-index), and the group-by-time interaction.

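### The SAP does not exclude study-administered PHQ-9/GAD-7 scores from the depression and anxiety matching flags, so for an unknown share of collaborative-care patients the flags are ascertained more completely than in controls

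*SAP*

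**What the plan says.** The comparison of patients rests on matching. SAP 5 states: "Baseline variables in the propensity score model were age at index event date, sex, race/ethnicity, average MEDD, anxiety, depression, and Charlson comorbidity index score". Of the two psychiatric flags and the comorbidity index it says: "Anxiety, depression, and Charlson comorbidity scores were determined from pre-index encounter diagnoses, historical problem lists, and PHQ-9/GAD-7 scores" above 10 in the health record. It does not say whether the pre-index limit also applies to the scores or whether study-collected scores count. The propensity model contains no score value and no indicator that a score was ever taken.

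In the collaborative-care arm, study procedure can generate the scores:

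- Protocol C.4.2: "Eligibility criteria for stepped opioid CCM include PHQ-9 or GAD-7" of 10 or more, alongside a clinical diagnosis and other items.
- Protocol Appendix A, Interested Patients Workflow, step 3: staff telephone self-referring patients and "invite them to complete the screening assessment with the PHQ9 and GAD7". Under step 4, the physician is notified about eligibility when "the study team/CHW-administered PHQ9/GAD7 score meets the threshold", which is 10 or more on either scale.
- SAP 5: "For the behavioral health group, the index date was defined as the date of enrollment during the study recruitment period". The self-referral screen comes before the physician's referral, so it would normally fall before the index date.

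For controls, no study procedure generates them:

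- SAP 5: "Potential participants in the control arm of the study were identified from the chronic opioid health maintenance registry". No score is required.
- Protocol C.4.3: medical assistants are expected to give registry patients the PHQ-4, which does not set the flag.
- Protocol C.4.1: after a PHQ-4 of 3 or more, documenting the two longer scales "is recommended for detailed screening and subsequent monitoring of symptoms should a formal diagnosis be made". Protocol C.4.4 leaves usual care to the physician's discretion.

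Protocol C.1 requires a diagnosis of depression or anxiety of all study patients. The SAP's definition of controls does not repeat this.

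**The concern.** Matching is meant to make patients who were not individually randomised comparable. If a matching variable is recorded more completely in one arm, and the extra recording comes from recruitment, equal flags need not mean equal patients. A self-referred patient with symptoms but no coded diagnosis can be flagged by the study's own screen, while a control with the same symptoms and no charted score is coded as having neither condition. A balance table would not show this, because it compares the flags themselves.

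The consequence depends on the outcome. Dose and service use are analysed by difference-in-difference, which removes stable differences in level. The first-documentation outcomes (pain agreement, urine drug screen, naloxone, specialist referral) are assessed only after the index date, in patients without earlier documentation, with study group as the only model term. I take the new-antidepressant outcome to be handled in the same way, since SAP 1.4.1 words it alike. For these outcomes nothing but the matching adjusts for baseline differences. If diagnosed and undiagnosed patients differ in how often such items are newly documented, the group odds ratio carries that difference.

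**Working it through.** The plan gives no figure to reproduce. The mechanism follows from the text above; its size can only be illustrated.

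**Inputs**

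- 245 per group: SAP 4.
- u, share of collaborative-care patients flagged by a study score alone: not given; assumed 5%, 10%, 25%, 40%.
- r, share of undiagnosed symptomatic controls with a charted score: not given; assumed 0 or 30%.
- Probability of a first documentation with no programme effect: not given; assumed 30% in diagnosed patients and p_u = 15% or 20% in undiagnosed patients.
- 150 per group: assumed, because SAP 5 drops patients with earlier documentation and the analysed number must fall below the full sample.

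**Formulas**

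- Collaborative-care rate: a = u·p_u + (1−u)·0.30.
- Undiagnosed share of matched flagged controls: s = u·r/(u·r + 1 − u).
- Control rate: c = s·p_u + (1−s)·0.30.
- Null odds ratio: OR = [a/(1−a)]/[c/(1−c)].
- Standard error of ln OR: SE = √{1/[n·a(1−a)] + 1/[n·c(1−c)]}.
- With d = ln OR/SE, two-sided error = Φ(−1.96−d) + Φ(−1.96+d).

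**Worked case** (u = 25%, r = 0, p_u = 15%): a = 0.25×0.15 + 0.75×0.30 = 0.2625; c = 0.30; OR = (0.2625/0.7375)/(0.30/0.70) = 0.83; ln OR = −0.186. With n = 245, SE = 0.201, d = −0.92 and the error is 15%. With n = 150, SE = 0.257, d = −0.72 and the error is 11%.

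**All cases** (ranges run over p_u = 15% and 20%)

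| r | u | Null OR | Error, n = 245 | Error, n = 150 |
|---|---|---|---|---|
| 0 | 5% | 0.96–0.98 | 5% | 5% |
| 0 | 10% | 0.93–0.95 | 6–7% | 5–6% |
| 0 | 25% | 0.83–0.89 | 9–15% | 8–11% |
| 0 | 40% | 0.74–0.82 | 17–32% | 12–22% |
| 30% | 5% | 0.98 | 5% | 5% |
| 30% | 10% | 0.95–0.97 | 5–6% | 5% |
| 30% | 25% | 0.89–0.92 | 7–9% | 6–7% |
| 30% | 40% | 0.83–0.89 | 9–14% | 7–11% |

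An odds ratio below 1 here works against the programme. If undiagnosed patients had the higher rate of new documentation, the ratio would exceed 1.

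**Would it help to strip study scores from the flag in the main match?** Score-only entrants would then be matched to unflagged controls. Assume current symptoms in 30–50% of controls, a charted diagnosis in 75–90% of symptomatic and 40–50% of non-symptomatic controls, and charted scores in 10–50%. At the upper end, the symptomatic share of unflagged controls is 0.5×0.25×0.9/(0.5×0.25×0.9 + 0.5×0.5) = 0.1125/0.3625 = 31%. At the lower end it is 0.3×0.1×0.5/(0.3×0.1×0.5 + 0.7×0.6) = 0.015/0.435 = 3%. Symptomatic patients would be paired mostly with asymptomatic ones.

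**The case against.** The strongest objection is the diagnosis criterion in Protocol C.1. If every patient in both arms had a diagnosis, nobody would be flagged by a score alone and u would be zero. This stands as a reason to expect a small share, but it does not close the matter. The SAP does not apply the criterion to controls, and in the protocol's own query (C.3.2) 62% of chronic opioid patients had an active diagnosis, so 38% did not. Appendix A step 4 mentions only the score. The criterion also asks for depression or anxiety, while the SAP uses two separate flags: a patient diagnosed with one can acquire the other from a study score.

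Stronger readings are tempting, but the documents do not support them:

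- A reader might infer that the whole collaborative-care arm is study-scored before the index date. Staff screening ahead of referral is described only for self-referral. Physician-referred patients may qualify on usual-care scores, and the baseline scoring of all referred patients (C.4.2) follows referral and may not be pre-index.
- A reader might infer that controls go unscreened. Registry patients are expected to have a PHQ-4, and the longer scales are recommended after a positive one, so r = 0 is an extreme.
- A reader might infer bias in the primary outcome, MEDD of 50 or more. None is shown: the analysis is difference-in-difference, pre-index average MEDD is a matching variable, and bias would require the unbalanced characteristic to affect change over time.
- A reader might take 32% as the expected error. It needs the extreme value of every input and the full 245 per group, which the first-documentation analyses cannot have if any patient has earlier documentation.

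**Conclusion.** The point holds as a gap in how two matching variables are ascertained. It concerns an unknown, possibly small, share of collaborative-care patients, and it matters chiefly for the first-documentation outcomes. At 5–10% score-only patients the effect is slight: a null odds ratio of 0.93 to 0.98 and an error of 5–7%. At 25–40% it is material: 0.74 to 0.92, with an error of 7–32% at 245 per group or 6–22% at 150. These figures rest on assumed shares and event rates and, for the smaller sample, an assumed size. They treat only patients flagged by a score alone, not those who gain a second flag. The documents fix neither size nor direction.

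It is also not established that the timing of recording explains most of any difference in current symptoms. Under the assumptions used above for unflagged controls, with symptoms in 30% and a charted diagnosis in 75% of symptomatic and 50% of other controls, raising score charting from 10% to every control lifts the symptomatic share of flagged controls only from 40% to 46%. An old diagnosis and a current score set the same flag, and equal recording does not cure that.

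**What to change.** In SAP 5, add a rematched analysis limited to patients in both arms who have an encounter or problem-list diagnosis of depression or anxiety dated before first study contact (screening call, self-referral or referral). Set both flags from those coded sources only and exclude study-administered scores. For controls, who have no study contact, date the diagnosis before the index date.

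Report by arm the share flagged by each source and the share with any PHQ-9/GAD-7 on record, so that the reader can see how large u and r are. State whether the pre-index limit covers the scores. Reconcile the flag's cut-off (above 10) with the entry threshold (10 or more), since a score of exactly 10 can support entry without setting the flag. Keep the first-documentation conclusions only if they agree with the rematched analysis.

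Do not simply unflag score-only entrants in the main match, for the reason shown in the working.

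The cost is one more matching run on data already in the record, and a smaller matched set with wider intervals. The analysis equalises how the flags are recorded, not how severe current symptoms are.

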At end of study, generalized linear mixed models will be used to assess average daily opioid dose defined as a binary indicator of ≥ 50 mg morphine equivalent dose and as a continuous measure. The outcomes will be assessed as pre-enrollment to post-enrollment changes in the EMR CDS + opioid BHI-CCM enrolled patients versus those in the usual care setting. Models will incorporate relevant covariates and design effects.

C.8.2. Aim 2 – Cost Effectiveness Analysis

All analyses will follow the guidelines on cost-effectiveness analysis conducted alongside clinical trials and economic modeling.(47) Our primary analysis will be based on the cohort of patients assigned the baseline characteristics of the participants in the proposed trial. Because of the chronic, recurrent nature of opioid

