## 1.2 Main Study Outcomes

### 1.3 Primary

**1.3.1** Odds Ratio of average morphine equivalent daily dose (MEDD) of opioid prescription  $\geq 50$  mg between study groups

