#### **4. Anticipated Effect Size, Power and Sample Size**

In the investigators' prior study on the clinical effectiveness of electronic medical record clinical decision support (EMR-CDS usual care) for opioid prescribing, approximately 20% of patients on chronic opioid therapy had an average daily opioid dose  $\geq 50$  MEDD. Using equal baseline response rate (RR) for the usual care and behavioral health collaborative care groups, a total sample size of 372 patients are required to detect an odds ratio of 2.25, corresponding to a 50% decrease in the collaborative care group (RR=10% vs 20% in usual care), with 80% power. The total sample size averaged 11 patients in each study group within each of 35 clinics. In accordance with the cluster randomized design, the variance inflation factor  $1 + (m - 1)\rho$  was incorporated, where  $m$  is the average cluster size ( $m=11$ ) and  $\rho$  is the intra-cluster correlation coefficient ( $\rho \leq 0.03$ ). Applying this inflation factor and rounding up to allow for equal group sizes across clusters resulted in a total sample size of 490 patients - 245 per group. Accounting for a potential 15% attrition rate, 578 total patients - 289 per group - were needed to attain the target sample size required to detect a 50% decrease in proportion of patients with average daily opioid dose  $\geq 50$  MEDD in the collaborative care group compared to the usual care group.

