Repeat measured outcomes include average MEDD,  $\text{MEDD} \geq 50$ ,  $\text{MEDD} \geq 90$ , and service utilization (inpatient/emergency department). These repeated outcomes are evaluated using the generalized linear mixed model approach described above with fixed effects as defined for the model. MEDD categorial outcomes are evaluated via mixed effects logistic regression models with estimates of odds ratios and difference-in-difference ratios (ratio of odds ratios). Mixed effects negative binomial regression models are used for assessing group differences in service utilization with rate ratios and difference-in-difference ratios (ratio of rate ratios).

Outcomes defined by first-time documentation of guideline concordant care for opioid risk mitigation are also evaluated using logistic regression. These outcomes are not repeated measures as they are only assessed post-index among patients with no pre-index documentation. Thus, time effects and random patient effects are omitted from the generalized linear model when evaluating new occurrences of guideline concordant care for opioid risk mitigation. The resulting logistic regression models include a single fixed effect for study group and no random effects.

Analyses were carried out using SAS version 9.4 for Windows, group comparisons are evaluated at significance level 0.05, and all estimates are presented with 95% confidence intervals.

**Ochsner Clinic Foundation  
Institutional Review Board**  
[name]  
[contact] | [[contact]](mailto:[contact])  

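### The primary MEDD ≥50 model has no clinic-level variance term, although the sample was inflated 1.30-fold for clinic clustering; the effect on type I error runs from none to about 11%, depending on how the arms spread over clinics

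*SAP*

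**What the plan says.** SAP 1.3 defines the primary outcome as an odds ratio between study groups: "Odds Ratio of average morphine equivalent daily dose (MEDD) of opioid prescription" at or above 50 mg.

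SAP section 4 sizes the trial on that outcome. It starts from 372 patients and continues: "In accordance with the cluster randomized design, the variance inflation factor" 1 + (m − 1)ρ, with m = 11, ρ at most 0.03, and 35 clinics. The result is 490, then 578 after 15% attrition.

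SAP section 5 describes the model in two sentences. On random effects: "All outcome models for repeated measures incorporate a random effect with unstructured covariance matrix to model within-patient variability". On fixed effects: "The model included fixed effects for study group, time (pre-index, post-index), and the group-by-time interaction". It then applies this model to average MEDD, MEDD ≥50, MEDD ≥90 and inpatient and emergency use: "These repeated outcomes are evaluated using the generalized linear mixed model approach described above with fixed effects as defined for the model". It names no clinic, provider or region term and no cluster-robust variance.

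Protocol C.8.1 closes its Aim 1 analysis paragraph with: "Models will incorporate relevant covariates and design effects". It does not say which effects.

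This point covers the repeated-measure models only. The logistic models for first-time documentation of guideline care, which the SAP says have no random effects, are left aside.

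**The concern.** The patient random effect accounts for one patient's pre-index and post-index values being alike. It does nothing about patients of the same clinic being alike. The plan judged that second correlation large enough to add about 118 patients (490 − 372), and then specifies a test that sets it to zero.

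This would be harmless if both arms were drawn evenly from the same clinics, because a shared clinic effect then cancels from the group contrast. Several features of the design make that uncertain:

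- On siting, Protocol C.4.2 says: "We will physically locate the service in the 5 clinic locations with the highest opioid prescription rates".
- Under Protocol C.4.3, only physicians who agree to take part see the referral prompt.
- Under Protocol C.4.4, patients enter by referral or self-referral.
- Under SAP section 5, controls come from the health-system opioid registry by propensity-score matching, and neither clinic nor region is in the propensity model.

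The difference-in-difference removes only the part of a clinic's effect that stays constant from pre- to post-index. If prescribing habits drift at clinic level over an enrolment window running from April 2019 to December 2021, and the arms sit in different clinics, that drift enters the group-by-time term with a standard error that ignores it.

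**Working it through.** **1. The plan's own figures.**
- The rates 20% and 10% give an odds ratio of (0.20/0.80)/(0.10/0.90) = 2.25, as stated.
- A log-odds-ratio formula with pooled rate 0.15, two-sided 0.05 and 80% power gives N = 4(1.960 + 0.842)²/[0.15 × 0.85 × (ln 2.25)²] = 374, against the stated 372.
- Inflation: 1 + (11 − 1) × 0.03 = 1.30. Then 372 × 1.30 = 483.6, rounded up to 490 = 35 × 14.
- Attrition: 245/0.85 = 288.2, so 289 per group and 578 in total.
- The value m = 11 matches 372/35 = 10.6, the total per clinic, although the SAP describes it as per study group. This does not affect the point.

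**2. Power.** By the same formula, N = 490 gives 80.3% with the 1.30 factor applied and 89.3% without it. The SAP claims 80%, so its claim stands.

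**3. The model as specified.** logit P(MEDD ≥50) = b0 + b1·group + b2·time + b3·group×time + patient effect. At clinic level this is a design effect of 1, where the sizing used 1.30.

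**4. Error of a test that ignores clinic.** Take 245 patients per arm and 35 clinics. Let pI and pC be the shares of each arm in a given clinic. The variance of the group contrast, relative to what the model assumes, is

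D = (1 − ρ) + ρ · Σ(pI − pC)² / (2/245),

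and the actual two-sided error is 2[1 − Φ(1.96/√D)]. With 5 hubs and 30 other clinics, each group of clinics sharing its patients evenly, Σ(pI − pC)² = d²(1/5 + 1/30), where d is the difference in hub share between the arms. The hub shares are assumptions, because the documents do not give them.

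| Enrolled from hubs / controls from hubs | ρ | D | Type I error |
|---|---|---|---|
| same mix | 0.03 | 0.97 | 4.7% |
| 50% / 30% | 0.03 | 1.00 | 5.05% |
| 50% / 20% | 0.03 | 1.05 | 5.5% |
| 75% / 40% | 0.03 | 1.075 | 5.9% |
| 75% / 20% | 0.03 | 1.23 | 7.7% |
| 100% / 20% | 0.03 | 1.52 | 11.2% |
| 75% / 20% | 0.01 | 1.08 | 5.9% |

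Example, 75%/20% at ρ = 0.03: d = 0.55; 0.3025 × 0.2333 = 0.0706; 0.0706 × 122.5 = 8.65; D = 0.97 + 0.03 × 8.65 = 1.23; 1.96/√1.23 = 1.77; error 7.7%.

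**5. Check on the contrast actually tested.** The formula uses ρ as if it applied to the pre/post change. A simulation of the change in a binary outcome checks this (20% prevalence, binary ICC 0.03, assumed within-patient latent correlation 0.8, z-test ignoring clinic). With the clinic effect's correlation over time assumed to be 0.5 and then 0.8, rejection rates were:
- same mix: 5.2% and 5.1%
- 75% hub: 7.8% and 6.0%
- 100% hub: 12.5% and 8.8%

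The formula's figures for the hub cases fall inside or close to these ranges. The more stable the clinic effect, the smaller the excess.

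**The case against.** The strongest reply is that the plan describes a layout in which the problem vanishes. Protocol C.8.1 has an average of 7 patients per study group in each of 35 clinics. SAP section 4 speaks of each group within each clinic and of equal group sizes across clusters. Protocol C.4.2 lets every clinic in a region refer. With equal clinic mix the error is 4.7%, slightly conservative. This stands as a statement of intent, but these are sizing averages. Nothing in the enrolment or matching rules enforces them.

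A reader might go further and infer that the standard error is 12% too small (1/√1.30 = 0.877) and the test runs at 8.6%, by putting 1.30 straight into the error formula. The documents do not support this. The 1.30 factor describes a single-time comparison of arms in separate clusters. The SAP's contrast is a difference-in-difference, and no text places the arms in separate clinics. A reader might also infer that the trial lacks the power it claims. It does not: the claim is 80%, and the clustered calculation returns 80.3%.

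Three further objections are fair. The hub shares are assumed, and modest changes bring the excess down to a point or less. The randomised unit is the region (SAP section 3), so a clinic term alone does not reflect the randomisation. And a logistic model with patient, clinic and clinic-by-period effects, two observations per patient and about 14 patients per clinic may fail to converge or return zero variances. The fix has to deal with the last two.

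The Protocol's sentence on design effects does not answer the point. It is generic, and the SAP's explicit list of terms does not carry it through.

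**Conclusion.** The omission is real: the plan sizes for clinic clustering and then specifies a primary model, and four companion models, without it. Whether the primary interval is too narrow is not settled by the documents. At the ICC ceiling of 0.03, the actual type I error is about 5% with equal clinic mix, about 5.5 to 8% with 50 to 75% of enrolled patients from the hubs against 20% of controls, and about 11% in the extreme case (9 to 12% in simulation). A lower ICC, a higher hub share among controls, or clinic effects that are stable over time bring it back towards 5%. These figures rest on assumed hub shares and an even spread within hub and non-hub clinics. The model as specified cannot show which case applies. That is the reason to change it, even though the harm may prove small.

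**What to change.** In SAP section 5, for MEDD ≥50, MEDD ≥90, average MEDD and utilisation:

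- Keep the patient effect, and base the primary interval and p-value on a clinic-aware variance. Use either clinic-clustered standard errors with a small-sample correction, or a clinic random intercept plus a clinic-by-period random effect.
- If the mixed model is chosen, name the clustered standard errors as the fallback should it fail to converge or estimate a zero variance.
- Add region as a fixed effect with its period interaction, or as a stated sensitivity analysis, because region is the randomised unit.
- Report the estimated clinic ICC beside the assumed 0.03, and the number of patients per arm in each clinic.
- Reconcile the text with the design-effects sentence in Protocol C.8.1.

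The cost is SAP wording and a few SAS statements, with no new patients or data. The interval would be about 14% wider on the plan's own factor (√1.30 = 1.14) and close to unchanged if the arms are balanced within clinics. If most enrolled patients sit in five clinics, the small-sample correction has less information than 35 clinics suggests, and the report should say so. The change corrects the variance only. It does not remove selection or confounding between hub and other clinics.
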